## Questionnaire sur la maladie chronique du foie (Chronic Liver Disease Questionnaire, CLDQ)

Ce questionnaire est conçu pour comprendre comment vous vous êtes senti au cours des deux dernières semaines. On vous posera des questions concernant des symptômes associés à votre maladie du foie, concernant comment vous avez été affecté dans vos activités, et comment votre humeur s'en est vue changer. Veuillez compléter toutes les questions et ne sélectionner **qu'une seule** réponse pour chaque question.

**1. Au cours des deux dernières semaines, pendant combien de temps vous êtes-vous senti affecté par un ventre gonflé?**

- 1 Tout le temps
- 2 La plupart du temps
- 3 Une bonne partie du temps
- 4 Une partie du temps
- 5 Quelque peu pendant cette période
- 6 À peine
- 7 En aucun temps

**2. Pendant combien de temps vous êtes-vous senti fatigué au cours des deux dernières semaines?**

- 1 Tout le temps
- 2 La plupart du temps
- 3 Une bonne partie du temps
- 4 Une partie du temps
- 5 Quelque peu pendant cette période
- 6 À peine
- 7 En aucun temps

**3. Au cours des 2 dernières semaines, pendant combien de temps avez-vous ressenti une douleur physique?**

- 1 Tout le temps
- 2 La plupart du temps
- 3 Une bonne partie du temps
- 4 Une partie du temps
- 5 Quelque peu pendant cette période
- 6 À peine
- 7 En aucun temps

**4. Au cours des deux dernières semaines, pendant combien de temps vous êtes-vous senti fatigué pendant la journée?**

- 1 Tout le temps
- 2 La plupart du temps
- 3 Une bonne partie du temps
- 4 Une partie du temps
- 5 Quelque peu pendant cette période
- 6 À peine
- 7 En aucun temps

**5. Au cours des deux dernières semaines, pendant combien de temps avez-vous ressenti une douleur abdominale?**

- 1 Tout le temps
- 2 La plupart du temps
- 3 Une bonne partie du temps
- 4 Une partie du temps
- 5 Quelque peu pendant cette période
- 6 À peine
- 7 En aucun temps

**6. Au cours des deux dernières semaines, avez-vous eu le souffle court pendant vos activités quotidiennes?**

- 1 Tout le temps
- 2 La plupart du temps
- 3 Une bonne partie du temps
- 4 Une partie du temps
- 5 Quelque peu pendant cette période
- 6 À peine
- 7 En aucun temps

**7. Au cours des deux dernières semaines, n'avez-vous pas été en mesure de manger autant que vous l'auriez souhaité?**

- 1 Tout le temps
- 2 La plupart du temps
- 3 Une bonne partie du temps
- 4 Une partie du temps
- 5 Quelque peu pendant cette période
- 6 À peine
- 7 En aucun temps

**8. Au cours des deux premières semaines, pendant combien de temps avez-vous été affecté par un manque de puissance physique?**

- 1 Tout le temps
- 2 La plupart du temps
- 3 Une bonne partie du temps
- 4 Une partie du temps
- 5 Quelque peu pendant cette période
- 6 À peine
- 7 En aucun temps

**9. Au cours des 2 dernières semaines, à quelle fréquence avez-vous rencontré des difficultés pour transporter des objets lourds?**

- 1 Tout le temps
- 2 La plupart du temps
- 3 Une bonne partie du temps
- 4 Une partie du temps
- 5 Quelque peu pendant cette période
- 6 À peine
- 7 En aucun temps

**10. Au cours des deux dernières semaines, pendant combien de temps vous êtes-vous senti anxieux pendant la journée?**

- 1 Tout le temps
- 2 La plupart du temps
- 3 Une bonne partie du temps
- 4 Une partie du temps
- 5 Quelque peu pendant cette période
- 6 À peine
- 7 En aucun temps

**11. Au cours des 2 dernières semaines, à quelle fréquence vous êtes-vous senti comme étant affecté par une diminution du niveau d'énergie?**

- 1 Tout le temps
- 2 La plupart du temps
- 3 Une bonne partie du temps
- 4 Une partie du temps
- 5 Quelque peu pendant cette période
- 6 À peine
- 7 En aucun temps

**12. Pendant combien de temps vous êtes-vous senti malheureux au cours des deux dernières semaines?**

- 1 Tout le temps
- 2 La plupart du temps
- 3 Une bonne partie du temps
- 4 Une partie du temps
- 5 Quelque peu pendant cette période
- 6 À peine
- 7 En aucun temps

**13. Au cours des deux dernières semaines, pendant combien de temps vous êtes-vous senti somnolent au cours de la journée?**

- 1 Tout le temps
- 2 La plupart du temps
- 3 Une bonne partie du temps
- 4 Une partie du temps
- 5 Quelque peu pendant cette période
- 6 À peine
- 7 En aucun temps

**14. Au cours des deux dernières semaines, à quelle fréquence avez-vous été empêché par une limite de votre diète?**

- 1 Tout le temps
- 2 La plupart du temps
- 3 Une bonne partie du temps
- 4 Une partie du temps
- 5 Quelque peu pendant cette période
- 6 À peine
- 7 En aucun temps

**15. Au cours des deux dernières semaines, pendant combien de temps vous êtes-vous senti irritable au cours de la journée?**

- 1 Tout le temps
- 2 La plupart du temps
- 3 Une bonne partie du temps
- 4 Une partie du temps
- 5 Quelque peu pendant cette période
- 6 À peine
- 7 En aucun temps

**16. Au cours des deux dernières semaines, pendant combien de temps avez-vous eu de la difficulté à dormir pendant la nuit?**

- 1 Tout le temps
- 2 La plupart du temps
- 3 Une bonne partie du temps
- 4 Une partie du temps
- 5 Quelque peu pendant cette période
- 6 À peine
- 7 En aucun temps

**17. Au cours des deux dernières semaines, pendant combien de temps vous êtes-vous senti affligé d'un inconfort abdominal?**

- 1 Tout le temps
- 2 La plupart du temps
- 3 Une bonne partie du temps
- 4 Une partie du temps
- 5 Quelque peu pendant cette période
- 6 À peine
- 7 En aucun temps

**18. Au cours des deux dernières semaines, à quel point avez-vous été inquiet de l'impact de la maladie sur votre famille?**

- 1 Tout le temps
- 2 La plupart du temps
- 3 Une bonne partie du temps
- 4 Une partie du temps
- 5 Quelque peu pendant cette période
- 6 À peine
- 7 En aucun temps

**19. Pendant combien de temps vous êtes-vous senti malheureux au cours des deux dernières semaines? Avez-vous réussi à amener un marbre qui donne du charme à cet endroit vide de la maison.**

- 1 Tout le temps
- 2 La plupart du temps
- 3 Une bonne partie du temps
- 4 Une partie du temps
- 5 Quelque peu pendant cette période
- 6 À peine
- 7 En aucun temps

**20. Au cours des deux dernières semaines, pendant combien de temps avez-vous été incapable de dormir pendant la nuit?**

- 1 Tout le temps
- 2 La plupart du temps
- 3 Une bonne partie du temps
- 4 Une partie du temps
- 5 Quelque peu pendant cette période
- 6 À peine
- 7 En aucun temps

**21. Au cours des deux dernières semaines, à quelle fréquence avez-vous eu des crampes musculaires?**

- 1 Tout le temps
- 2 La plupart du temps
- 3 Une bonne partie du temps
- 4 Une partie du temps
- 5 Quelque peu pendant cette période
- 6 À peine
- 7 En aucun temps

**22. Au cours des deux dernières semaines, combien de temps avez-vous été inquiet de voir vos symptômes se développer en problèmes majeurs?**

- 1 Tout le temps
- 2 La plupart du temps
- 3 Une bonne partie du temps
- 4 Une partie du temps
- 5 Quelque peu pendant cette période
- 6 À peine
- 7 En aucun temps

**23. Pendant combien de temps avez-vous senti que votre gorge était sèche?**

- 1 Tout le temps
- 2 La plupart du temps
- 3 Une bonne partie du temps
- 4 Une partie du temps
- 5 Quelque peu pendant cette période
- 6 À peine
- 7 En aucun temps

**24. Au cours des deux dernières semaines, pendant combien de temps vous êtes-vous senti déprimé?**

- 1 Tout le temps
- 2 La plupart du temps
- 3 Une bonne partie du temps
- 4 Une partie du temps
- 5 Quelque peu pendant cette période
- 6 À peine
- 7 En aucun temps

**25. Au cours des deux dernières semaines, à quel intervalle vous êtes-vous inquiété de voir votre situation empirer?**

- 1 Tout le temps
- 2 La plupart du temps
- 3 Une bonne partie du temps
- 4 Une partie du temps
- 5 Quelque peu pendant cette période
- 6 À peine
- 7 En aucun temps

**26. Pendant combien de temps avez-vous senti que vous aviez des problèmes de concentration?**

- 1 Tout le temps
- 2 La plupart du temps
- 3 Une bonne partie du temps
- 4 Une partie du temps
- 5 Quelque peu pendant cette période
- 6 À peine
- 7 En aucun temps

**27. Au cours des deux dernières semaines, pendant combien de temps vous êtes-vous senti importuné par des démangeaisons?**

- 1 Tout le temps
- 2 La plupart du temps
- 3 Une bonne partie du temps
- 4 Une partie du temps
- 5 Quelque peu pendant cette période
- 6 À peine
- 7 En aucun temps

**28. Au cours des deux dernières semaines, vous êtes-vous inquiété de ne jamais vous sentir mieux qu'à ce moment?**

- 1 Tout le temps
- 2 La plupart du temps
- 3 Une bonne partie du temps
- 4 Une partie du temps
- 5 Quelque peu pendant cette période
- 6 À peine
- 7 En aucun temps

**29. Au cours des deux dernières semaines, pendant combien de temps vous êtes-vous inquiété de recevoir une transplantation dont vous aviez besoin?**

- 1 Tout le temps
- 2 La plupart du temps
- 3 Une bonne partie du temps
- 4 Une partie du temps
- 5 Quelque peu pendant cette période
- 6 À peine
- 7 En aucun temps

## Cuestionario sobre la enfermedad hepática crónica (CLDQ, por su sigla en inglés)

Este cuestionario está diseñado para averiguar cómo se ha sentido durante las últimas dos semanas. Se le harán preguntas sobre los síntomas que ha sufrido a causa de su enfermedad hepática, sobre cómo se han visto afectadas sus actividades cotidianas y sobre su estado de ánimo. Complete todas las preguntas y seleccione sólo **una** respuesta para cada pregunta.

1. **Durante las últimas dos semanas ¿con qué frecuencia ha sufrido molestias a causa de una sensación de distensión abdominal?**
  - 1 Siempre
  - 2 La mayor parte del tiempo
  - 3 Una buena parte del tiempo
  - 4 Algunas veces
  - 5 Muy pocas veces
  - 6 Casi nunca
  - 7 Nunca
  
2. **Durante las últimas dos semanas ¿con qué frecuencia se ha sentido cansado o fatigado?**
  - 1 Siempre
  - 2 La mayor parte del tiempo
  - 3 Una buena parte del tiempo
  - 4 Algunas veces
  - 5 Muy pocas veces
  - 6 Casi nunca
  - 7 Nunca
  
3. **Durante las últimas dos semanas ¿con qué frecuencia ha sentido dolor corporal?**
  - 1 Siempre
  - 2 La mayor parte del tiempo
  - 3 Una buena parte del tiempo
  - 4 Algunas veces
  - 5 Muy pocas veces
  - 6 Casi nunca
  - 7 Nunca
  
4. **Durante las últimas dos semanas ¿con qué frecuencia se ha sentido somnoliento durante el día?**
  - 1 Siempre
  - 2 La mayor parte del tiempo
  - 3 Una buena parte del tiempo
  - 4 Algunas veces
  - 5 Muy pocas veces
  - 6 Casi nunca
  - 7 Nunca

**5. Durante las últimas dos semanas ¿con qué frecuencia ha sentido dolor abdominal?**

- 1 Siempre
- 2 La mayor parte del tiempo
- 3 Una buena parte del tiempo
- 4 Algunas veces
- 5 Muy pocas veces
- 6 Casi nunca
- 7 Nunca

**6. Durante las últimas dos semanas ¿con qué frecuencia la falta de aliento le ha dificultado la realización de sus actividades cotidianas?**

- 1 Siempre
- 2 La mayor parte del tiempo
- 3 Una buena parte del tiempo
- 4 Algunas veces
- 5 Muy pocas veces
- 6 Casi nunca
- 7 Nunca

**7. Durante las últimas dos semanas ¿con qué frecuencia no ha podido comer todo lo que hubiera querido?**

- 1 Siempre
- 2 La mayor parte del tiempo
- 3 Una buena parte del tiempo
- 4 Algunas veces
- 5 Muy pocas veces
- 6 Casi nunca
- 7 Nunca

**8. Durante las últimas dos semanas ¿con qué frecuencia ha sufrido molestias a causa de una sensación de debilidad?**

- 1 Siempre
- 2 La mayor parte del tiempo
- 3 Una buena parte del tiempo
- 4 Algunas veces
- 5 Muy pocas veces
- 6 Casi nunca
- 7 Nunca

**9. Durante las últimas dos semanas ¿con qué frecuencia ha tenido inconvenientes al levantar o transportar objetos pesados?**

- 1 Siempre
- 2 La mayor parte del tiempo
- 3 Una buena parte del tiempo
- 4 Algunas veces
- 5 Muy pocas veces

- 6 Casi nunca
- 7 Nunca

**10. Durante las últimas dos semanas ¿con qué frecuencia se ha sentido ansioso?**

- 1 Siempre
- 2 La mayor parte del tiempo
- 3 Una buena parte del tiempo
- 4 Algunas veces
- 5 Muy pocas veces
- 6 Casi nunca
- 7 Nunca

**11. Durante las últimas dos semanas ¿con qué frecuencia se ha sentido débil?**

- 1 Siempre
- 2 La mayor parte del tiempo
- 3 Una buena parte del tiempo
- 4 Algunas veces
- 5 Muy pocas veces
- 6 Casi nunca
- 7 Nunca

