**8. How much of the time in the last two weeks have you been bothered by having decreased strength?**

- 1 All of the time
- 2 Most of the time
- 3 A good bit of the time
- 4 Some of the time
- 5 A little of the time
- 6 Hardly any of the time
- 7 None of the time

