**11. How often during the last 2 weeks have you felt a decreased level of energy?**

- 1 All of the time
- 2 Most of the time
- 3 A good bit of the time
- 4 Some of the time
- 5 A little of the time
- 6 Hardly any of the time
- 7 None of the time

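### Spanish CLDQ item 11 asks about feeling weak, close to Spanish item 8, where the English and French forms ask about energy, so Fatigue scores are not fully comparable across language forms

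*Protocol*

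**What the plan says.** Protocol Appendix 12.3 prints the CLDQ in English, French and Spanish. The English form keeps two ideas apart. Item 8 reads "How much of the time in the last two weeks have you been bothered by having decreased strength" and item 11 reads "How often during the last 2 weeks have you felt a decreased level of energy". French item 11 also asks about energy: "à quelle fréquence vous êtes-vous senti comme étant affecté par une diminution du niveau d'énergie".

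In the Spanish form, item 8 asks "con qué frecuencia ha sufrido molestias a causa de una sensación de debilidad", that is, how often the subject was troubled by a feeling of weakness. Item 11 asks "11. Durante las últimas dos semanas ¿con qué frecuencia se ha sentido débil", that is, how often the subject felt weak. The two items use the noun and the adjective of the same word.

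SAP 8.3 assigns items 2, 4, 8, 11 and 13 to Fatigue. It takes the plain average of the items in each domain and then averages the six domain scores for the overall score. The CLDQ is an exploratory endpoint, analysed by ANCOVA with the baseline value as covariate. Neither the scoring nor the model makes any provision for form language.

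**The concern.** The scoring treats item 11 as the same question on every form. On the Spanish form it is close to a second asking of item 8, and both items fall in the same domain. A Spanish-form subject's Fatigue score therefore gives more weight to weakness, and has no item directly about energy. Scores from different language forms are then pooled as if they measured the same five things. What is at stake is the comparability of the Fatigue domain, and to a small extent of the overall CLDQ score. HVPG, the key secondary endpoints, the sample size and the type I error rate are not touched.

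**Working it through.** **1. The scoring map.** The SAP 8.3 domains hold 3 (abdominal), 5 (fatigue), 5 (systemic), 3 (activity), 8 (emotional) and 5 (worry) items. 3 + 5 + 5 + 3 + 8 + 5 = 29, and each item from 1 to 29 is used exactly once. This reproduces the 29 questions in Protocol 6.3.1, so the map itself is sound.

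**2. Item 8 and item 11 side by side.**

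| Form | Item 8 | Item 11 |
|---|---|---|
| English | reduced strength | reduced energy |
| French | lack of physical power | reduced energy |
| Spanish | bothered by a feeling of weakness | felt weak |

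None of the 29 Spanish items mentions energy.

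**3. Weights.** One Fatigue item carries 1/5 = 20% of the domain. In the overall score it carries 1/6 × 1/5 = 1/30 = 3.3%.

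| | English form | Spanish form |
|---|---|---|
| Strength or weakness, share of Fatigue | 1/5 = 20% | 2/5 = 40% |
| Energy asked directly, share of Fatigue | 1/5 = 20% | 0/5 = 0% |
| Strength or weakness, share of overall score | 1/30 = 3.3% | 2/30 = 6.7% |

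**4. Effect on one subject's score.** Let *w* be the answer to the weakness wording of item 11 and *e* the answer the subject would have given to an energy wording. The shift is (*w* − *e*)/5 in Fatigue and (*w* − *e*)/30 in the overall score.

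- Gap of 1 point: 1/5 = 0.20 in Fatigue and 1/30 = 0.033 overall.
- Largest possible gap on a 1-to-7 scale, 6 points: 6/5 = 1.2 and 6/30 = 0.2.

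The sign follows that of *w* − *e*. If weakness and energy are answered alike, the shift is zero.

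**5. Effect on a trial mean.** Multiply by the share of subjects who use the Spanish form. The documents do not give it. With an assumed share of 5% to 20% and a mean gap of 1 point, the shift in the Fatigue mean is 0.20 × 0.05 = 0.01 to 0.20 × 0.20 = 0.04. In the overall score it is 0.05/30 = 0.002 to 0.20/30 = 0.007. These are sizes in either direction. A gap that is the same in all arms, with the same Spanish share in each, cancels in the treatment contrast.

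**The case against.** **The Spanish wording may be deliberate.** The documents do not say where the Spanish form came from or whether it is a validated translation; Protocol 6.3.1 cites reliability and validity for the CLDQ in general only. Translations need not be literal, and rewriting one item of a validated form could do harm. This stands as a reason to check the source before changing the text. It does not remove the difference in content seen on the page.

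**The items are not identical, and the domain still covers related ground.** Item 8 asks about being bothered by weakness; item 11 asks how often the subject felt weak. Item 2, on being tired or fatigued, remains on the Spanish form and may pick up part of a change in energy. The English domain also has overlapping items: item 4 on sleepiness and item 13 on drowsiness. All of this stands. A reader might infer that the Spanish form counts one answer twice and cannot register a change in energy. The documents support only that two of five items concern weakness and none asks directly about energy.

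**French is an imperfect comparator.** French item 4 asks about daytime tiredness where the English asks about sleepiness. The point therefore rests on the English form; the French agreement on item 11 is only supporting evidence.

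**No direction or bias is shown.** A reader might infer that the Spanish form understates a benefit. That needs felt weakness to stay put while energy improves. If both move together the loss approaches zero, and if weakness improves more the sign reverses. Allocation is randomised and the analysis adjusts for baseline, so bias between arms does not follow either.

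**Conclusion.** The concern holds as a matter of comparability. Spanish item 11 departs from the English in content, and the SAP's scoring turns that into a different weighting of the Fatigue domain for Spanish-form subjects. The effect is 0.20 in Fatigue and 0.033 in the overall score for each point of gap between the weakness and energy answers, with no established sign. The individual-level figures follow from the SAP's own scoring rules. The trial-level range of 0.01 to 0.04 rests on an assumed 5% to 20% Spanish share and a 1-point mean gap, and could be close to zero. The endpoint is exploratory, so this is a minor point, worth making because the correction is cheap.

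**What to change.** Check Spanish item 11 against the source translation, then correct it so that it asks about reduced energy, as the English item does.

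If forms have already been completed, record the language of each form and add one sensitivity analysis to SAP 8.3. Score Fatigue from items 2, 4, 8 and 13 for all subjects, in every language, at both CLDQ visits (Infusion Visits 1 and 26). Leaving out Spanish-form subjects is an alternative. Four of five items, 80%, is also above the SAP's threshold of more than 50% for scoring a domain.

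Do not set item 11 to missing on Spanish forms alone. That still leaves no energy item there, and it gives each remaining item 1/4 = 25% of Fatigue against 20% on English forms, so subjects would still be scored on different item sets.

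Cost: one sentence in the Spanish form, a language field if none exists, and a line in the SAP. The Fatigue score in the sensitivity analysis is slightly less precise because it uses four items instead of five.

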**12. Durante las últimas dos semanas ¿con qué frecuencia se ha sentido triste?**

- 1 Siempre
- 2 La mayor parte del tiempo
- 3 Una buena parte del tiempo
- 4 Algunas veces
- 5 Muy pocas veces
- 6 Casi nunca
- 7 Nunca

**13. Durante las últimas dos semanas ¿con qué frecuencia se ha sentido somnoliento?**

- 1 Siempre
- 2 La mayor parte del tiempo
- 3 Una buena parte del tiempo
- 4 Algunas veces
- 5 Muy pocas veces
- 6 Casi nunca
- 7 Nunca

**14. Durante las últimas dos semanas ¿con qué frecuencia se ha sentido molesto a causa de una limitación en su dieta?**

- 1 Siempre
- 2 La mayor parte del tiempo
- 3 Una buena parte del tiempo
- 4 Algunas veces
- 5 Muy pocas veces
- 6 Casi nunca

7 Nunca

**15. Durante las últimas dos semanas ¿con qué frecuencia ha estado irritable?**

- 1 Siempre
- 2 La mayor parte del tiempo
- 3 Una buena parte del tiempo
- 4 Algunas veces
- 5 Muy pocas veces
- 6 Casi nunca
- 7 Nunca

**16. Durante las últimas dos semanas ¿con qué frecuencia ha tenido dificultad para dormir por la noche?**

- 1 Siempre
- 2 La mayor parte del tiempo
- 3 Una buena parte del tiempo
- 4 Algunas veces
- 5 Muy pocas veces
- 6 Casi nunca
- 7 Nunca

**17. Durante las últimas dos semanas ¿con qué frecuencia ha sufrido molestias a causa de una sensación de malestar abdominal?**

- 1 Siempre
- 2 La mayor parte del tiempo
- 3 Una buena parte del tiempo
- 4 Algunas veces
- 5 Muy pocas veces
- 6 Casi nunca
- 7 Nunca

**18. Durante las últimas dos semanas ¿con qué frecuencia ha estado preocupado por la repercusión que tiene su enfermedad hepática en su familia?**

- 1 Siempre
- 2 La mayor parte del tiempo
- 3 Una buena parte del tiempo
- 4 Algunas veces
- 5 Muy pocas veces
- 6 Casi nunca
- 7 Nunca

**19. Durante las últimas dos semanas ¿con qué frecuencia ha sufrido cambios bruscos de ánimo?**

- 1 Siempre
- 2 La mayor parte del tiempo

- 3 Una buena parte del tiempo
- 4 Algunas veces
- 5 Muy pocas veces
- 6 Casi nunca
- 7 Nunca

**20. Durante las últimas dos semanas ¿con qué frecuencia no ha podido quedarse dormido por la noche?**

- 1 Siempre
- 2 La mayor parte del tiempo
- 3 Una buena parte del tiempo
- 4 Algunas veces
- 5 Muy pocas veces
- 6 Casi nunca
- 7 Nunca

**21. Durante las últimas dos semanas ¿con qué frecuencia ha sufrido calambres musculares?**

- 1 Siempre
- 2 La mayor parte del tiempo
- 3 Una buena parte del tiempo
- 4 Algunas veces
- 5 Muy pocas veces
- 6 Casi nunca
- 7 Nunca

**22. Durante las últimas dos semanas ¿con qué frecuencia ha estado preocupado por la posibilidad de que sus síntomas se conviertan en problemas más graves?**

- 1 Siempre
- 2 La mayor parte del tiempo
- 3 Una buena parte del tiempo
- 4 Algunas veces
- 5 Muy pocas veces
- 6 Casi nunca
- 7 Nunca

**23. Durante las últimas dos semanas ¿con qué frecuencia ha tenido la boca reseca?**

- 1 Siempre
- 2 La mayor parte del tiempo
- 3 Una buena parte del tiempo
- 4 Algunas veces
- 5 Muy pocas veces
- 6 Casi nunca
- 7 Nunca

**24. Durante las últimas dos semanas ¿con qué frecuencia se ha sentido deprimido?**

- 1 Siempre
- 2 La mayor parte del tiempo

- 3 Una buena parte del tiempo
- 4 Algunas veces
- 5 Muy pocas veces
- 6 Casi nunca
- 7 Nunca

**25. Durante las últimas dos semanas ¿con qué frecuencia ha estado preocupado por la posibilidad de que su enfermedad empeore?**

- 1 Siempre
- 2 La mayor parte del tiempo
- 3 Una buena parte del tiempo
- 4 Algunas veces
- 5 Muy pocas veces
- 6 Casi nunca
- 7 Nunca

**26. Durante las últimas dos semanas ¿con qué frecuencia ha tenido dificultad para concentrarse?**

- 1 Siempre
- 2 La mayor parte del tiempo
- 3 Una buena parte del tiempo
- 4 Algunas veces
- 5 Muy pocas veces
- 6 Casi nunca
- 7 Nunca

**27. Durante las últimas dos semanas ¿con qué frecuencia ha sufrido molestias a causa de picazón?**

- 1 Siempre
- 2 La mayor parte del tiempo
- 3 Una buena parte del tiempo
- 4 Algunas veces
- 5 Muy pocas veces
- 6 Casi nunca
- 7 Nunca

**28. Durante las últimas dos semanas ¿con qué frecuencia ha estado preocupado por la posibilidad de que usted nunca se sienta mejor?**

- 1 Siempre
- 2 La mayor parte del tiempo
- 3 Una buena parte del tiempo
- 4 Algunas veces
- 5 Muy pocas veces
- 6 Casi nunca
- 7 Nunca

**29. Durante las últimas dos semanas ¿con qué frecuencia ha estado preocupado por la disponibilidad de un hígado si usted llegara a necesitar un trasplante?**

- 1 Siempre
- 2 La mayor parte del tiempo
- 3 Una buena parte del tiempo
- 4 Algunas veces
- 5 Muy pocas veces
- 6 Casi nunca
- 7 Nunca

